#### **6.4.2.2 Paternal exposure**

Male subjects should refrain from fathering a child or donating sperm during the study and for 12 weeks following the last dose.

Pregnancy of the subject's partner is not considered to be an AE. However, the outcome of all pregnancies (spontaneous miscarriage, elective termination, ectopic pregnancy, normal birth, or congenital abnormality) should, if possible, be followed up and documented.

The outcome of any conception occurring from the date of the first investigational product administration until 12 weeks after the last investigational product administration should be followed up and documented. Information on the pregnancy of a subject's partner must be obtained directly from the subject's partner. Therefore, prior to obtaining information about the pregnancy, the Investigator must obtain the consent of the subject's partner.

### **6.5 Adverse events of special interest**

An AESI is an AE of scientific and medical concern specific to understanding biologics and requires close monitoring and rapid communication by the Investigator to the Sponsor/Sponsor's delegate. An AESI may be serious or nonserious.

Adverse events of special interest in this protocol will be assessed at each visit on the CRF. The events of interest are medically significant infections (non-opportunistic serious infections and opportunistic infections including viral infection/reactivation), severe hypersensitivity reactions including anaphylaxis and immune complex disease, malignancy, *herpes zoster* with cutaneous presentation, TB (including latent TB), influenza, vasculitis (non SLE), and MACE (including stroke, myocardial infarction, or cardiovascular death). Lupus nephritis (associated with SLE; WHO or ISN/RPS Classification Class III, IV or V) is defined

not as an AESI but as a new SLEDAI AE, and diagnosis will be supported with laboratory results.

An AESI that meets 1 of the seriousness outcomes listed in Section 6.2 will be categorised as an SAE for the purposes of follow-up responsibility and safety reporting. A nonserious AESI will be categorised as an AE. For reporting of AESIs, see Section 6.8.

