#### 3.3.2.1 Background Systemic Lupus Erythematosus standard of care medications (oral corticosteroids, antimalarials, and immunosuppressants)

Permitted SOC medications for SLE during the LTE study include OCS (up to 40 mg/day of prednisone or equivalent [REDACTED]), antimalarials, and immunosuppressants (methotrexate, mycophenolate mofetil/mycophenolic acid, mizoribine, azathioprine, and tacrolimus).

Investigators should apply local practices for safety monitoring, eg, by serum chemistry tests, in case SOC dose is changed, eg, increased, and/or new disease-modifying antirheumatic drug (DMARD) is added.

Subjects may undergo changes in their background SOC medication for SLE (OCS, antimalarials, or immunosuppressants) doses, based on the opinion of the Investigator. On treatment days, changes in doses will commence after all assessments have been completed and the investigational product has been administered. There is no minimum dose requirement for background SOC medications for SLE, and subjects may taper off as permitted by disease activity. Due to variability in subject responses to background SOC medications for SLE and tolerability of taper, Investigators are asked to use their clinical judgment with respect to the taper schedule. If the subject experiences an increase in SLE disease activity, SOC medications for SLE may be adjusted according to the Investigator's clinical judgment, but may not exceed maximally permitted doses as defined by exclusionary criteria.

All permitted SOC SLE therapies received from randomisation through the end of the study will be recorded on the source document and CRF, and will include the specific indication for use (eg, general SLE activity, skin involvement, nephritis, pleurisy) as well as the dose, start and stop dates, frequency, and route of administration. In addition, any change in permitted SOC SLE therapy and the reason for change must be documented.

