### 5.2.8 Modified Flare Index

A modified SELENA flare index, using the SLEDAI-2K instead of the SELENA SLEDAI, will be completed at the times indicated in the Study Plan (Table 2 and Table 3) to characterise flares as safety events [REDACTED].

The modified flare assessment should be completed by the Investigator or delegated/qualified physician as per protocol schedule of assessments. Assessment of flare should be scored in comparison to the subject's previous visit (ie, over the past 28 days) and should only include findings that, in the opinion of the Investigator, are due to SLE disease activity within that timeframe. Flare will be defined as any 1 criterion present in either the Mild/Moderate Flare or Severe Flare categories. New or worsened manifestations should only be reported for manifestations of SLE.

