#### **6.6.6 Adverse events based on examinations and tests**

The results from protocol-mandated laboratory tests and vital signs will be summarised in the Clinical Study Report. Deterioration as compared to baseline in protocol-mandated laboratory values, vital signs, ECGs, and other safety assessments should therefore only be reported as AEs if they fulfil any of the SAE criteria or are the reason for discontinuation of treatment with the investigational product.

If deterioration in a laboratory value/vital sign is associated with clinical signs and symptoms, the sign or symptom will be reported as an AE and the associated laboratory result/vital sign will be considered as additional information. Wherever possible, the reporting Investigator will use the clinical rather than the laboratory term (eg, anaemia versus low haemoglobin value). In the absence of clinical signs or symptoms, clinically relevant deteriorations in non-mandated parameters should be reported as AE(s).

Deterioration of a laboratory value, which is unequivocally due to disease progression, should not be reported as an AE.

Any new or aggravated clinically relevant abnormal medical finding at a physical examination as compared with the baseline assessment will be reported as an AE (or SAE, as appropriate).

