#### **6.6.7 Disease progression/worsening of systemic lupus erythematosus**

Disease progression can be considered as a worsening of a subject's condition attributable to SLE. It may be an increase in the activity or severity of the existing manifestations of SLE or the appearance of new manifestations. Worsening of SLE should not be reported as an AE, unless the signs and symptoms meet criteria for an SAE.

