#### Severe flare

A severe flare is defined if at least one of the following criteria are met:

- Increase from previous visit in SLEDAI-2K of  $\geq 7$  points
- At least 1 new or worse manifestation in
  - Central nervous system SLE
  - Vasculitis
  - Nephritis
  - Myositis
  - Haemolytic anaemia  
defined as haemoglobin  $< 70$  g/L or decrease in haemoglobin  $> 30$  g/L with positive Coombs AND at least 1 of the following: decreased haptoglobin, increased total bilirubin not due to Gilbert's disease, increased reticulocyte count
- Hospitalization due to SLE disease activity
- Increase from previous visit in PGA to a value  $> 2.5$  points

The flare rate per subject year will be calculated separately for mild/moderate flares and severe flares as well as overall. The flare rate per subject year is defined as the number of subjects with a respective flare divided by the sum of exposure time in days (i.e., date of last dose of investigational product + 28 days - day of first dose of investigational product + 1 day) for all subjects in the analysis set multiplied by 365.25 days/year.

For analyses based on LTE data only (e.g. for subjects switching from Placebo to 300 mg anifrolumab in the “All Anifrolumab” treatment group), the first administration of investigational product during the LTE will be considered in the above. For analyses based on feeder study data only (e.g. for subjects switching from Placebo to 300 mg anifrolumab in the “All Randomised Placebo” treatment group), the minimum of last administration of investigational product in the feeder study + 28 days and first administration of investigational product in the LTE -1 day will be used in the above. If a subject discontinued the study or had the last follow-up visit earlier than expected, the date of study discontinuation/end of study will be used as the censoring date.

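### Protocol 6.5 makes Class III–V lupus nephritis an adverse event, but 6.6.7 tells sites not to report it as one unless it is serious, and no visible text says which section prevails.

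*Protocol*

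**What the plan says.** Protocol 6.5, after listing the AESIs, deals separately with one renal diagnosis, lupus nephritis of Class III, IV or V on either of two named classifications. The section treats this condition "not as an AESI but as a new SLEDAI AE, and diagnosis will be supported with laboratory results". It sets no seriousness threshold. The label new SLEDAI AE is not explained or used elsewhere in the visible text.

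Protocol 6.6.7 covers worsening lupus. It describes disease progression broadly: "It may be an increase in the activity or severity of the existing manifestations of SLE or the appearance of new manifestations". The reporting rule follows: "Worsening of SLE should not be reported as an AE, unless the signs and symptoms meet criteria for an SAE". Meeting an SAE criterion is the only exception.

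Protocol 6.6.6 has a related rule for laboratory findings: "Deterioration of a laboratory value, which is unequivocally due to disease progression, should not be reported as an AE".

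SAP 4.2.1.1 summarises any AE, AEs of severe intensity and AEs leading to discontinuation of investigational product, alongside the primary AESI and SAE summaries. The visible SAP has no nephritis category and no rule for choosing between the two protocol sections.

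**The concern.** A new Class III–V nephritis that meets no SAE criterion is the diagnosis named in 6.5 and also a new manifestation of lupus under 6.6.7. A site working from 6.5 records an AE. A site that opens 6.6.7, the section titled for worsening lupus, is told not to. Both have followed the protocol.

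At stake is the completeness of the secondary safety description. The SAP builds the all-AE, severe-AE and AE-leading-to-discontinuation rates from what sites record. A non-serious nephritis may be severe in intensity, since 6.6.3 keeps severity and seriousness apart, and it may lead to stopping treatment. Section 6.5 shows that the sponsor wanted this diagnosis recorded as an AE, and 6.6.7 as written can defeat that.

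**Working it through.** **1. The two rules applied to the same event**

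| Event in the extension study | Under 6.5 | Under 6.6.7 | Agree? |
|---|---|---|---|
| New Class III–V nephritis, meets an SAE criterion | AE, and an SAE | Reported, as an SAE | Yes |
| New Class III–V nephritis, meets no SAE criterion | AE | Not reported as an AE | No |

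Only the second row is in conflict. Such an event is neither an AESI nor an SAE under either section, so the primary outcome is the same whichever is followed.

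**2. What other data would show**

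- Flare index. Nephritis is a severe-flare criterion in SAP 3.1.5. Protocol 5.2.8 scores flare against the previous visit, glossed as the past 28 days. Tables 2 and 3 schedule it after baseline at Weeks 12, 24, 36, 52, 76, 104, 128 and 156. Read literally, 8 × 28 = 224 of 1092 treatment days are covered (224 / 1092 = 20.5%). A site that scored change since the last flare assessment would cover more. SAP 4.2.1.5 reports flares as mild/moderate, severe or any, so nephritis is not separately visible.
- Medication records. Protocol 3.3.2.1 requires the indication for each permitted lupus therapy, with examples that include nephritis: "general SLE activity, skin involvement, nephritis, pleurisy". This is a trace of the event, not an AE record.

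**3. Exposure governed by these sections**

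Protocol 8.2 plans about 893 subject-years for Randomised Anifrolumab 300 mg and 517 for Randomised Placebo. Under 8.3.3 both run from randomisation in the feeder studies. Under 6.6.1, events before randomisation in the extension are reported in the feeder studies, so 6.5 and 6.6.7 govern extension time only.

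To split the totals I assume 360 subjects in each of these two arms and 90 on 150 mg (back-solved, not stated), with dropout at mid-year. The stated inputs are annual dropout of 20% on 300 mg and 30% on placebo or 150 mg, and 90% entry. A year contributes starters × (1 − dropout/2).

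- Anifrolumab 300 mg: feeder 360 × 0.90 = 324. Entrants 360 × 0.80 × 0.90 = 259.2. Extension 259.2 × 0.90 × (1 + 0.80 + 0.64) = 569.2. Total 893.2 (stated 893).
- Placebo: feeder 360 × 0.85 = 306. Entrants 360 × 0.70 × 0.90 = 226.8, half of them (113.4) to placebo. Extension 113.4 × 0.85 × (1 + 0.70 + 0.49) = 211.1. Total 517.1 (stated 517).
- All Anifrolumab, with 20% dropout once on 300 mg: 893.2 + 90 × 0.85 (76.5) + 150 mg switchers 56.7 × 0.90 × 2.44 (124.5) + placebo switchers 113.4 × 0.90 × 2.44 (249.0) = 1343.2 (stated 1343).

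All three totals are reproduced. Implied entry is 259.2 + 226.8 + 56.7 = 542.7, a little below the planned 575. Scaling by 575 / 542.7 = 1.06 gives about 603 and 224 subject-years, which barely changes the counts below.

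**4. Illustrative size**

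Assumptions, neither from the documents: 10 new Class III–V cases per 1000 subject-years, 30–70% of them non-serious.

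- Anifrolumab 300 mg: 569 × 0.010 = 5.7 cases; × 0.3 to 0.7 = 1.7 to 4.0 affected.
- Placebo: 211 × 0.010 = 2.1 cases; × 0.3 to 0.7 = 0.6 to 1.5 affected.

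The counts scale with the assumed incidence. Half of it gives 0.9–2.0 and 0.3–0.7; double gives 3.4–8.0 and 1.3–3.0.

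**The case against.** The best defence is that the specific rule overrides the general one. Section 6.5 names a single, histologically classed condition; 6.6.7 is a general instruction. Many readers would take the first as an exception to the second. That is reasonable, but neither section refers to the other, and a site that consults only 6.6.7 sees no exception. The defence shows what the sponsor probably meant, not that sites will act alike.

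Three further points stand and limit the concern.

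- The seriousness definition in 6.2 includes important medical events, so many Class III–V cases may qualify as SAEs and be recorded either way. The non-serious remainder may be small.
- Section 5.1 and other material are blacked out, so one can say only that no visible text settles the question.
- A reader might infer that 6.6.6 is a third conflicting rule. It is not. It excludes a deteriorating laboratory value, not a diagnosis, and asks for the clinical rather than the laboratory term. That fits 6.5, where laboratory results support the diagnosis.

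**Conclusion.** The contradiction between 6.5 and 6.6.7 is real and should be reconciled, but its reach is limited. It concerns non-serious new Class III–V nephritis arising in the extension study, and it affects the all-AE, severe-AE and AE-leading-to-discontinuation summaries. The true size is unknown. On the assumptions shown, roughly 2–4 of 6 cases on anifrolumab 300 mg and about 1 of 2 on placebo would depend on the section a site follows.

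Four stronger readings are tempting, and the documents do not support them.

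- *The primary safety result is compromised.* It rests on AESIs and SAEs, and this event is neither under either section.
- *The cases are lost to the study.* They may be missing from AE data, yet some will appear as severe flares or medication indications.
- *The assumed rate can be applied to the full 893 and 517 subject-years.* That would count feeder time, which is governed by AE rules that are not in these documents.
- *One arm is favoured by design.* Under Protocol 3.8 investigators and site staff stay blinded, so undercounting and site-to-site noise are the more likely result.

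**What to change.** Add one sentence to Protocol 6.6.7: Exception: new lupus nephritis Class III, IV or V is recorded as an AE as defined in Section 6.5, serious or not. Add a cross-reference to 6.6.7 in 6.5. Section 6.6.6 needs no change. Keep the wording to new nephritis: extending it to recurrent disease would go beyond 6.5 and is for the sponsor to decide.

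If the SAP tabulates a rate, present it by LTE treatment group on extension data only, using the lupus nephritis preferred term. The combined treatment groups would mix events recorded under possibly different rules, in unequal proportions: on the split above, feeder time is 306 / 517 = 59% of Randomised Placebo but 324 / 893 = 36% of Randomised Anifrolumab 300 mg. The AE variables in 6.6.3 include no nephritis class, so the row should not be defined by class.

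The cost is one sentence, one cross-reference and, optionally, one table row, with no new assessments. If data collection is already complete, the row can still be added and the ambiguity stated as a limitation in the study report.

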### **6.5.1 Medically significant infections (including viral infection/reactivation/opportunistic infections)**

Medically significant infections are an important potential risk based on the mechanism of action of anifrolumab. For safety reporting purposes, in this study, infections are classified as either serious non-opportunistic infections or opportunistic infections as described here.

#### **6.5.1.1 Serious non-opportunistic infection**

A serious non-opportunistic infection is any non-opportunistic infection that meets the SAE criteria in Section 6.2. Serious non-opportunistic infection AEs are reported as SAEs and AESIs. It is expected that culture results and all diagnostic or therapeutic procedure results performed on a subject experiencing a serious non-opportunistic infection will be provided as an SAE update. Nonserious non-opportunistic infections will not be captured as AESIs.

#### **6.5.1.2 Opportunistic infection**

An opportunistic infection is an invasive infection caused by microorganisms that are normally non-pathogenic or rarely pathogenic in individuals with normal immune function or cause an infection of a type or severity not seen in the normal host.

Examples of opportunistic infections that may occur in SLE subjects include: *herpes zoster* meningoencephalitis, *Salmonella* bacteraemia, *Pneumocystis jirovecii* pneumonia, or progressive multifocal leukoencephalopathy. It is expected that culture results and all diagnostic or therapeutic procedure results performed on a subject experiencing a serious opportunistic infection will be provided as an SAE update. Since anifrolumab is an immunomodulatory agent and the Sponsor needs to understand the safety profile of this investigational product, including assessment of how anifrolumab may affect resistance to different types of infections, Investigators are asked to undertake appropriate microbiologic identification including culture, and report culture results for all subjects who develop serious infections.

#### **6.5.1.3 Influenza**

Influenza is a severe viral infection that includes the following symptoms: temperature greater than 100.8°F (38.2°C), and malaise, headache, or myalgia. It is often accompanied by nausea, vomiting, and diarrhoea, and at least 1 of the following respiratory symptoms: cough, sore throat, or shortness of breath.

Laboratory criteria for influenza include at least 1 of the following: isolation of influenza virus from a clinical specimen, detection of influenza virus nucleic acid in a clinical specimen,

identification of influenza virus antigen by direct fluorescent antibody test in a clinical specimen, OR influenza-specific antibody response.

A confirmed case of influenza meets the clinical and laboratory criteria for the viral illness. Laboratory confirmation should be done using locally available, rapid, commercial tests approved by regulatory agencies and sampling respiratory specimens. Not all upper respiratory viral infections or gastrointestinal viral infections are influenza. In the case where a subject reports a viral infection severe enough to be considered, in the opinion of the Investigator, influenza, a viral test should be performed (if possible) to confirm the diagnosis. If, in the opinion of the Investigator, the subject has had influenza (the specific viral infection), this should be reported as an AESI, whether or not a test to confirm the diagnosis has been performed. Less severe viral infection should be reported as an AE only.

#### **6.5.2 Severe hypersensitivity reactions including anaphylaxis and immune complex disease**

Anaphylaxis is a severe, potentially fatal, systemic allergic reaction that occurs suddenly after contact with an allergy-causing substance, such as investigational product. For the purposes of this study, the definition [REDACTED] is provided as a simple and rapid means to make the diagnosis of anaphylaxis during infusion with investigational product. This definition was a product of a symposium convened by the National Institute of Allergy and Infectious Diseases and Food Allergy and Anaphylaxis Network ([Sampson et al, 2006](#)).

#### **6.5.3 Malignancy**

Malignancy is a neoplasm characterised by cells with abnormal features, uncontrolled rapid growth with invasive and/or metastatic tendencies diagnosed based on pathologic and clinical standards. Understanding risk of developing different malignancies is critical to establishing the benefit: risk profile for anifrolumab. Investigators are therefore requested to obtain biopsy results and pertinent biomarker and/or genetic testing results performed, and to report these for any malignancies reported during the study.

#### **6.5.4 Herpes zoster reactivations (including cutaneous events)**

*Herpes zoster* is a viral infection characterised by a cutaneous vesicular eruption on an erythematous base presenting along dermatome(s) and usually associated with prodromal pain. *Herpes zoster* results from the reactivation of *varicella zoster* virus; multiple dermatomes may be involved (>3 indicates disseminated disease) and organ or systemic infection may occur (invasive; therefore an opportunistic infection). Polymerase chain reaction testing of samples from vesicles, biopsy, or other specimens (eg, cerebrospinal fluid) may confirm the presence of *varicella zoster* virus. Herpes Zoster reactivation with cutaneous presentation is an identified risk.

. Systemic infections or other medically significant herpes zoster infections are considered important potential risks and classified as *medically significant infections* for adverse event reporting in this study unexpected for regulatory reporting purposes. For additional information regarding *herpes zoster*, refer to the IB. As all herpes zoster events are considered to be an AESI, the Sponsor will collect information including whether or not

subjects have received vaccination for *herpes zoster*. The *herpes zoster* vaccine medical history data will be captured in the appropriate sections of the CRF.

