If an AE has a missing onset date, then unless the stop date of the AE indicates otherwise, it will be considered an AE in the categories above. Similarly, if an AE has a partial onset date, then unless the partial onset date or the stop date indicates otherwise, it will be considered an AE in the categories above. If the missing or partial start date does not allow an assignment of the event as during the Phase 3 feeder studies or the LTE study, the AE will be assigned to the study in which it was documented.

Adverse events of special interest are marked as such in the electronic Case Report Form (eCRF).

Major acute cardiovascular events (MACEs) will be determined according to the assessments of the Cardiovascular Event Adjudication Committee (CV-EAC).

An infusion-related reaction (as assessed by the investigator) is defined as an AE with a preferred term of “Infusion related reaction”.

An infection is defined as an AE within the MedDRA system organ class infections and infestations.

Opportunistic infections are those marked in the eCRF as assessed by the investigator as opportunistic and non-opportunistic infections are all infections not marked as opportunistic by the investigator.

Hypersensitivity is defined as adverse events with MedDRA preferred term (PT) = “Hypersensitivity” and Lower level term (LLT) = “Hypersensitivity reaction”.

Herpes zoster is further classified according to the information given on the Herpes zoster log as follows:

Category	Rash [Y/N]	Episode status of HZ Event [localized/ disseminated]	Specify Disseminated [cutaneous/ systemic]	Any organ involvement [Y/N]
Cutaneous (localised) herpes zoster	Y	Localized	[no rule]	N
Cutaneous disseminated herpes zoster	Y	Disseminated	Cutaneous	[no rule]
Visceral disseminated herpes zoster	[no rule]	Disseminated	Systemic	[no rule]

A COVID-19 related adverse event is defined as an AE with one of the following preferred terms: “Asymptomatic COVID-19”, “Congenital COVID-19”, “Coronavirus infection”, “Coronavirus pneumonia”, “Coronavirus test positive”, “COVID-19”, “COVID-19 pneumonia”, “Post-acute COVID-19 syndrome”, “SARS-CoV-2 antibody test positive”, “SARS-CoV-2 carrier”, “SARS-CoV-2 sepsis”, “SARS-CoV-2 test false negative”, “SARS-CoV-2 test positive”, “SARS-CoV-2 viraemia”, “Suspected COVID-19”, “Vaccine derived SARS-CoV-2 infection”.

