#### 4.2.1.1 Adverse events

Even not stated explicitly, all summaries described below will be based on AEs during treatment and follow-up.

An overall summary of subjects with at least 1 AE in the following categories will be presented as event rates per 100 subject years. This summary will also be presented for the additional supportive treatment groups placebo feeder + anifrolumab 300 mg LTE, and anifrolumab 150 mg feeder + anifrolumab 300 mg LTE. This summary will also be presented for the LTE Study only.

- Any AE
- Any AE with outcome = death
- Any SAE (including events with outcome = death)
- Any AE leading to discontinuation of investigational product
- Any AE related to investigational product
- Any AE of severe intensity
- Any AESI
  - Any AESI of non-opportunistic serious infections
  - Any AESI of opportunistic infections
  - Any AESI of anaphylaxis
  - Any AESI of malignancy
  - Any AESI of herpes zoster
  - Any AESI of tuberculosis
  - Any AESI of influenza
  - Any AESI of vasculitis (non SLE)
  - Any AESI of major acute cardiovascular events
- Any other significant AE

The overall summary above will be repeated for the sub-periods prior to the COVID-19 pandemic (events prior to 11-Mar-2020) and during the COVID-19 pandemic (events on or after the COVID-19 pandemic; only subjects remaining in the study on 11-Mar-2020 will be included). These summaries will be presented for the LTE study only. Alternative event rates and event rates will be computed. As sensitivity analysis the overall summary will be repeated including subjects excluded from analysis (see Section 4.1.1).

An overall summary of subjects with at least one COVID-19 related AE in the following categories will be presented as alternative event rates per 100 subject years. This summary will be presented for the LTE Study only. Only subjects remaining in the study on 11-Mar-2020 will be included.

- Any COVID-19 related AE

- Any COVID-19 related AE with outcome = death
- Any COVID-19 related SAE (including events with outcome = death)
- Any COVID-19 related AE leading to discontinuation of investigational product
- Any COVID-19 related AE related to investigational product
- Any COVID-19 related AE of severe intensity

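### The protocol gives two readings of the herpes zoster AESI and the SAP has no entry rule for it, so the zoster rate can vary by site and leave out systemic cases that are counted in another row

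*Protocol*

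**What the plan says.** The AESI list in Protocol 6.5 qualifies herpes zoster in a run that reads "with cutaneous presentation, TB (including latent TB), influenza, vasculitis (non SLE), and MACE". The same list has a separate class of medically significant infections, which covers serious non-opportunistic and opportunistic infections.

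Protocol 6.5.4 says "As all herpes zoster events are considered to be an AESI, the Sponsor will collect information". Just before that it says "Systemic infections or other medically significant herpes zoster infections are considered important potential risks and classified as *medically significant infections* for adverse event reporting", and it describes multi-dermatome disease in which "organ or systemic infection may occur (invasive; therefore an opportunistic infection". Protocol 6.5.1.2 names zoster meningoencephalitis as an example of an opportunistic infection. Protocol 1.3 has a third wording: cutaneous zoster together with other zoster-associated adverse events.

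Protocol 6.5.1.1 and 6.8 exclude infections that are neither serious nor opportunistic from AESI capture.

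SAP 3.1.1 says "Adverse events of special interest are marked as such in the electronic Case Report Form". It also takes opportunistic infections from the investigator's mark. It then subdivides zoster from a zoster log into localised cutaneous, cutaneous disseminated and visceral disseminated disease. SAP 4.2.1.1 has a row "Any AESI of herpes zoster" beside a separate row for opportunistic infections, both under any AESI. It also plans AESI rates by category and time interval, one Kaplan-Meier plot per AESI category, and a dedicated first-onset summary for zoster.

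**The concern.** AESI rates are part of the primary outcome, and zoster with cutaneous presentation is an identified risk of the drug (Protocol 1.3 and 6.5.4). The zoster row is therefore one that readers of the report will go to first.

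The protocol tells sites two things about which zoster events are zoster AESIs, and the SAP does not settle it. For other event types SAP 3.1.1 gives a rule that does not depend on how a site reads the protocol: a system organ class for infections, MedDRA terms for hypersensitivity, infusion-related reactions and COVID-19, and adjudication for MACE. Zoster has no such entry rule. Two sites with the same systemic case could mark it differently, and it could enter the zoster row at one and only the opportunistic-infection row at the other.

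There is also a conduct consequence. Protocol 6.8 sets a 72-hour reporting time for nonserious AESIs, so whether an event is an AESI at all decides whether that duty applies.

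**Working it through.** **1. The wordings side by side.**

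| Type of zoster event | Protocol 6.5 (with 6.5.1) | Protocol 6.5.4 | Row in the SAP |
|---|---|---|---|
| Localised, with rash | Zoster AESI | Zoster AESI | Zoster |
| With rash and systemic or organ disease | Zoster AESI, and also an opportunistic infection | AESI, classed as a medically significant infection | Zoster, opportunistic, or both, by eCRF mark |
| Systemic, without rash | AESI only through the infection class | AESI, classed as a medically significant infection | Zoster, opportunistic, or both, by eCRF mark |
| No cutaneous presentation, nonserious, not opportunistic | Not an AESI | AESI | Zoster or none, by eCRF mark |

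Only the last line is a strict conflict over AESI status. The two middle lines are a question of row: all readings make the event an AESI, but they do not agree on which row it belongs to, and the SAP does not say whether it may be in two.

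**2. Does the zoster log settle it?** It subdivides events already taken as zoster and does not say which events enter the AESI category. Its visceral disseminated category sets no condition on rash, so systemic zoster is evidently meant to be recognised as zoster. That shows the intent but is not an entry rule for the AESI row.

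**3. The plan's own figures.** Protocol 8.2 and SAP 1.3 expect 893 subject-years (Randomised Anifrolumab 300 mg) and 517 (Randomised Placebo), with an example rate of 10 per 1000.

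- Events: 893 × 10/1000 = 8.93 and 517 × 10/1000 = 5.17.
- Interval of Protocol 8.2: 10 × exp(±1.96 × √(1/8.93 − 1/893)) = 5.21 to 19.21, as stated. For 5.17 events in 517 subject-years it gives 4.24 to 23.58 (stated 4.24 to 23.57).
- Exact Poisson interval of SAP 4.1.3: lower = χ²(0.025; 2 × 8.93)/(2 × 893) × 1000 = 4.56; upper = χ²(0.975; 2 × 8.93 + 2)/(2 × 893) × 1000 = 19.03, as stated. For placebo it gives 3.33 to 23.03 (stated 3.32 to 23.03).

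The figures reproduce to rounding, and this point disputes none of them.

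**4. Sensitivity of the zoster row.** The documents give no zoster rate, so I borrow the example rate and round 8.93 to 9. The SAP rate counts subjects with an event, so read each count as a subject. Rate = n/893 × 1000, with exact 95% intervals.

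| Held only in another row | n | Rate per 1000 | 95% CI | Change |
|---|---|---|---|---|
| 0 | 9 | 10.08 | 4.61 to 19.13 | none |
| 1 | 8 | 8.96 | 3.87 to 17.65 | −11% |
| 2 | 7 | 7.84 | 3.15 to 16.15 | −22% |
| 3 | 6 | 6.72 | 2.47 to 14.62 | −33% |

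Each move takes 1/893 × 1000 = 1.12 per 1000 off the row. In Randomised Placebo, 5 of 517 is 9.67 per 1000 and 4 of 517 is 7.74, a fall of 20%. For these moves between AESI classes the any-AESI rate does not change. The SAE rate does not change either, because seriousness does not depend on AESI class.

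**The case against.** The protocol texts largely fit together. Protocol 6.5 lists medically significant infections as AESIs as well, so all zoster can be an AESI through two classes, and the wording in Protocol 1.3 points the same way. The 6.5.4 sentence on systemic zoster is about adverse event reporting rather than tabulation, and its text is visibly broken. Nothing says that the AESI rows exclude one another, and the eCRF is not available to check. The log has a place for visceral zoster. The first-onset summary in SAP 4.2.1.1 is for herpes zoster and is not limited to events ticked as AESIs. AESIs are also shown by preferred term, so a zoster term in another row would be visible.

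Most of this stands, and it rules out three stronger conclusions that a reader might draw.

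- *The rate of the identified risk loses its most serious cases.* Not supported. The identified risk is zoster with cutaneous presentation; systemic zoster is listed as an important potential risk. Only a case with both rash and systemic disease belongs to the identified risk and could still be placed elsewhere.
- *Under the 6.5 wording all systemic zoster leaves the zoster row.* Not supported. Section 6.5 asks for cutaneous presentation and does not exclude systemic involvement, so a systemic case with rash still meets it.
- *Systemic cases drop out of the primary outcome.* Not supported. They remain in any AESI, in the opportunistic or serious-infection row, and in the SAE tables if serious.

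What the objection does not supply is a rule. The log, the preferred-term display and the first-onset summary all leave open which events form the zoster AESI category, and the category rate and Kaplan-Meier curve need that settled.

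**Conclusion.** The point holds as a definition gap with a limited effect. The zoster AESI rate, its time-interval rates and its Kaplan-Meier curve rest on site marks made under two differing protocol wordings, with no term-based definition and no rule for events that fit two rows. They can vary by site and omit systemic zoster, with or without rash. The events are misplaced, not lost. Disagreement over whether an event is an AESI at all is confined to nonserious, non-opportunistic zoster without cutaneous presentation.

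The size is about 11% of the zoster row per subject moved, or 1.12 per 1000 subject-years, in Randomised Anifrolumab 300 mg. This assumes the example rate of 10 per 1000 and the planned 893 subject-years. Even three moves leave a rate inside the interval for the full count. A reader might want the number of cases likely to be misplaced, but the documents give neither a zoster rate nor the share that is systemic or without rash, so none can be given.

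**What to change.** In SAP 3.1.1, define the zoster category as any adverse event with a zoster or varicella zoster reactivation preferred term, or with a herpes zoster log entry, whichever AESI box is ticked. List the preferred terms. State that a systemic or visceral case counts in both the zoster and the opportunistic-infection rows and only once in any AESI. This goes beyond the investigator's mark for opportunistic infection, so the SAP should say so. Use the one definition for the AESI rates, the time-interval rates, the Kaplan-Meier plot and the first-onset summary in SAP 4.2.1.1.

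Protocol 6.5 and 6.5.4 must be reconciled. If the planned timetable held (last subject completed in Q3 2021; SAP version 5.0 is dated April 2022), a protocol change cannot alter how sites recorded events, so the SAP rule does the work.

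The cost is small: a definition in the SAP and a wording correction in the protocol, using data already collected. Some events will appear in two AESI rows and the zoster count may rise slightly. Any AESI would rise only through zoster events that sites had not marked as AESIs; a footnote should give their number.
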